11. DATA COLLECTION, QUALITY ASSURANCE, AND MANAGEMENT

11.1. Recording of Data

The study will use eCRFs for data collection. The data will be entered by trained site personnel only. The Investigator is responsible for ensuring that all sections of each eCRF are completed promptly and correctly and that the data can be verified against any source data.

Adverse events and medical history will be coded with the latest version of the Medical Dictionary for Regulatory Activities (MedDRA) available at study initiation. Similarly, prior and concomitant medications and concomitant therapies will be coded using the latest version of World Health Organization Drug Dictionary available at study initiation. The versions employed at study start will be maintained throughout the project.

11.2. Data Quality Assurance

To ensure compliance with Good Clinical Practices (GCP) and all applicable regulatory requirements, the Sponsor may conduct a quality assurance audit. See Section 11.4 for more details regarding this process.

11.3. Data Management

Data management will be performed by a qualified vendor under their standard operating procedures. The Sponsor will provide oversight.

11.4. Audits and Inspections

At any time prior to, during, or after completion of the clinical study, an audit or inspection may be performed by the Sponsor or designated representative, a regulatory authority, an IRB, or an IEC. The purpose of the audit or inspection is to systematically and independently examine all study-related activities and documents to determine whether these activities were conducted, and data were recorded, analyzed, and accurately reported according to the protocol, GCP guidelines of the International Council for Harmonisation (ICH), and any applicable regulatory requirements. The Investigator should contact the Sponsor immediately if contacted by a regulatory agency about an inspection. The Sponsor or a designated representative will be available to assist in the preparation of the study site for inspections. All pertinent study data will be made available for verification, audit, or inspection purposes.

12. STATISTICAL METHODS AND PLANNED ANALYSES

12.1. General Considerations

A Statistical Analysis Plan (SAP), specifying further details of the planned analyses, will be prepared and approved prior to lock of the database. This section presents a highlight of the approaches to be taken in performing the planned analyses.

Tabulations of summary statistics, graphical presentations, and statistical analyses will be performed using SAS® Software (Version 9.2 or higher). Descriptive statistics include mean, standard deviation (SD), median, minimum, and maximum for continuous variables, and frequency tables with counts and percentages for discrete variables.

Unless otherwise stated, “Baseline” will be defined as the last measurement obtained prior to the first dose of investigational product (pre-dose on Day 1). Hypothesis-testing will be performed at the 2-sided 5% significance level.

12.2. Determination of Sample Size

A total of 74 patients will provide approximately 80% power to detect a 3-point difference between treatment groups in the average change from Baseline scores from the PKAN-ADL, based on Student’s t-test with $\alpha = 0.05$ (2-sided); this calculation assumes a standard deviation of 4.5 points for the change from Baseline scores. Additional patients will be randomized to ensure that at least 74 patients complete the double-blind period with evaluable data (ie, having assessments at Baseline and Week 24 for the PKAN-ADL).

12.3. Analysis Sets

Double-Blind Period

Safety Population: The safety population will consist of all randomized patients who receive at least 1 dose of blinded investigational product. This population will be used for all summaries of patient accountability, demographic and Baseline data, and safety information, including AE incidence, for the double-blind period of the study.

Full Analysis Set (FAS): The FAS will consist of all randomized patients with at least 1 post-Baseline efficacy assessment. This population will serve as the basis for all efficacy analyses for the double-blind period of the study.

Open-Label Period

Safety Population: The safety population will consist of all patients who receive at least 1 dose of investigational product after entering the open-label period of the study. This population will be used for all summaries of patient accountability, demographic and Baseline data, and safety information, including AE incidence, for the open-label period of the study.

Full Analysis Set (FAS): The FAS will consist of all patients with at least 1 post-Baseline efficacy assessment in the open-label period of the study. This population will serve as the basis for efficacy analyses from the open-label period of the study.

12.4. Demographics and Baseline Characteristics

Demographic data (including age, race, ethnicity, gender, height, and weight), medical history (including PKAN-specific medical history), prior treatments, and pre-treatment clinical characteristics will be summarized by treatment group for the safety population using descriptive statistics.

12.5. Patient Accountability

All patients who meet all inclusion criteria and no exclusion criteria for the study, sign the informed consent form, and are enrolled and exposed to the investigational product will be accounted for in the safety analyses. Screen failures will not be accounted for in the data presentation.

Accountability tables will summarize the following information by treatment group: the number of patients randomized, the number included in each analysis population, the number evaluated at each study visit, the number discontinued from treatment by reason for treatment discontinuation, and the number discontinued from the study by reason for study discontinuation. A by-patient data listing of study completion information, including the timing and reason(s) for premature treatment discontinuation or study withdrawal, if applicable, will be presented.

12.6. Study Treatment Usage and Compliance

Compliance information collected via dispensed/returned investigational product unit counts will be summarized descriptively for each treatment group, including frequency tables to indicate the number of patients at least 80% compliant with the dosing regimen during the double-blind and open-label periods of the study.

12.7. Safety Analyses

Safety analyses will be performed using data from the safety population. Safety will be evaluated on the basis of treatment-emergent AEs (TEAEs), vital signs, weight, physical examinations, clinical laboratory assessments, C-SSRS, and ECG findings.

12.7.1. Physical Examination and Vital Signs

Vital signs and body weight will be summarized by treatment group using descriptive statistics. Summary statistics will be calculated for both the actual value and the change from Baseline value at each scheduled visit.

Pre-study physical examination abnormalities and physical examination abnormalities reported at the end of study will be tabulated by body system.

12.7.2. Clinical Laboratory Tests and Electrocardiograms

Clinical laboratory and ECG data will be summarized by treatment group using descriptive statistics based on the observed values and change from Baseline values at each scheduled visit. In addition, the number and percentage of patients with laboratory values that shift categories (ie, below/within/above normal range) will be tabulated at each study visit. Patients with clinically

significant changes from Baseline in laboratory values will be summarized and flagged in data listings.

12.7.3. Adverse Events

All AEs will be coded by Preferred Term and System Organ Class using the most recent version of MedDRA available at study initiation. By-patient listings of deaths, SAEs, and AEs leading to treatment discontinuation will be provided. The by-patient AE data listings will include onset and resolution dates, verbatim term, System Organ Class, Preferred Term, treatment, severity, relationship to treatment, action taken for the event, and outcome.

TEAEs in the double-blind period are defined as AEs that are new or are a worsening of an existing condition that begins from the day of first dose of investigational product until the day after the last dose for the double-blind treatment period. The incidence of TEAEs will be summarized for each treatment group by Preferred Term within body system, overall and by severity and relationship to treatment. Incidence calculations will be based on the numbers and percentages of patients with AEs. Although a MedDRA term may be reported more than once for a patient, that patient will be counted only once for that MedDRA term.

12.7.4. Open-Label Period

Safety data collected for the safety population during the open-label period of the study will be summarized using descriptive statistics, including summary tables of AEs, summary tables and graphical plots of mean values over time for continuous measurements (eg, vital signs, weight, laboratory evaluations), and frequency tables for categorical data obtained at each study visit. The last measurement obtained prior to the first dose of open-label investigational product will serve as the Baseline value for assessing change from Baseline during the open-label period of the study.

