Patients who permanently discontinue study medication early should be encouraged to continue study visits through Week 120 for continued collection of safety and efficacy data despite stopping study medication, but may withdraw consent at any time (see [Section 6.3.3](#)). Patients who agree to continue regularly scheduled study visits will complete the End of Treatment assessments listed in the schedule of events ([Section 15.1](#)) as close as possible to the patient's last dose of study medication. The visit data, including the primary reason for discontinuation of study medication, will be recorded on the End of Treatment eCRF. Subsequent study visit data will be recorded on the visit-specific eCRF, and the patient's final study visit will be recorded on the End of Treatment/Early Termination eCRF.

For patients who permanently discontinue study medication, the Investigator should resume standard of care treatment, including treatment with appropriate medications, as deemed necessary.

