10.5. Reporting Adverse and Serious Adverse Events

10.5.1. Reporting Adverse Events

AEs will be captured from the time the main study informed consent is signed to 30 days after the patient's last dose of investigational product or the patient's last scheduled visit, whichever occurs last.

- AEs should be recorded using appropriate medical terminology. When recording, it is preferable to provide a diagnosis. In the absence of a diagnosis, each sign and symptom should be captured as a unique AE. Sufficient information should be sought to assist the Investigator both in determining the diagnosis and in making a causality assessment.
- Reporting should not be delayed pending receipt of all required information. If information is unavailable at the time of the initial report, the Investigator is expected to follow-up until the required information has been obtained or until 30 days after the patient's last dose or last scheduled visit.

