4.11.1 Adverse Events (AEs)

All AEs will be coded by Preferred Term and System Organ Class using MedDRA coding dictionary Version 20.0.

TEAEs in the double-blind period are defined as AEs that are new or are a worsening of an existing condition that begin from the day of first dose of investigational product until the day after the last dose for the double-blind treatment period. TEAEs in the open-label period are defined as AEs that are new or are a worsening of an existing condition that begin from the day of first dose of open-label investigational product. TEAEs in the fosmetpantotenate safety population are defined as AEs that are new or are a worsening of an existing condition that begin from the day of first dose of (blinded or open-label) fosmetpantotenate.

An overview of adverse events will be provided for each of the three Safety Populations that summarizes incidence in the following categories, overall, by age group (pediatric, adult), and by sex:

- Any AEs
- Any TEAEs
- TEAEs by relationship to study medication (Not related, Unlikely Related, Possibly Related or Related)
- TEAEs by severity (mild, moderate, severe)

- Any TEAEs with an outcome of death
- TESAEs
- Treatment discontinuation due to TEAEs

The incidence of TEAEs will be summarized for each treatment group by Preferred Term as well as by Preferred Term within System Organ Class. The incidence of TEAEs by severity and relationship to treatment will be summarized for each treatment group by System Organ Class and Preferred Term. A patient with several occurrences of the same AE will be counted once and classified by the most severe event (or the event with the closest relationship to study drug). If severity or causality is missing, the worst case will be assumed (i.e., “Severe” if severity is missing and “Drug Related” if causality is missing.)

In addition, the incidence of Adverse Events of Interest (AEOIs), TESAEs, TEAEs leading to treatment discontinuation, and TEAEs leading to death will be summarized for each treatment group by System Organ Class and Preferred Term.

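### SAP 4.11.1 gives the open-label and Fosmetpantotenate Safety Population TEAE windows a start but no end, so adverse events beginning well after a patient has stopped the drug count as treatment-emergent

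*Protocol*

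**What the plan says.** SAP 4.11.1 defines three treatment-emergent windows in one paragraph.

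- **Double-blind:** events that "begin from the day of first dose of investigational product until the day after the last dose for the double-blind treatment period". Protocol 12.7.3 has the same end.
- **Open-label:** events new or worsening on an "existing condition that begin from the day of first dose of open-label investigational product". No end is stated.
- **Fosmetpantotenate Safety Population:** events new or worsening on an "existing condition that begin from the day of first dose of (blinded or open-label) fosmetpantotenate". No end is stated.

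The TEAE incidence tables are run on all three safety populations, as numbers and percentages of patients. For the open-label period the Protocol (12.7.4) says only "Safety data collected for the safety population during the open-label period of the study will be summarized" descriptively.

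Two Protocol rules determine how much off-drug time is observed. Under 6.5.4.2, patients who permanently stop the drug "should be encouraged to continue study visits through Week 120 for continued collection of safety and efficacy data despite stopping study medication". Under 10.5.1, "AEs will be captured from the time the main study informed consent is signed to 30 days after" the last dose or to the last scheduled visit, whichever is later. Protocol 6.3.1 also lets a patient count as a completer at Week 302 on or off drug.

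**The concern.** A treatment-emergent window should follow exposure. Here one of the three does and two do not, while the Protocol deliberately retains and observes patients who have stopped the drug. PKAN is progressive, and Protocol 6.5.4.2 returns these patients to standard care. Events arising from either source after exposure has ended would be counted as treatment-emergent in tables that have no concurrent placebo arm.

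These tables go into the interim report for regulators (SAP 4.3 and 4.11). In the same report, treatment duration stops at the last dose (SAP 4.9), so exposure and event counts would cover different stretches of time. Serious TEAEs and the severity tables use the same definitions.

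**Working it through.** The documents give no TEAE count or window length to reproduce, so the check compares rules and then does date arithmetic.

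**1. The windows side by side**

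| Table | Start | End stated |
|---|---|---|
| Double-blind | first blinded dose | last double-blind dose + 1 day |
| Open-label | first open-label dose | none |
| Fosmetpantotenate | first fosmetpantotenate dose, either period | none |

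**2. Is an end given elsewhere?**
- SAP 4.11 limits the open-label tables to open-label data and the fosmetpantotenate tables to data after first exposure. Neither limit refers to last dose.
- SAP 4.12.2 says that counting rules similar to the double-blind ones will apply to open-label safety. It states no end and does not mention the Fosmetpantotenate Safety Population.
- SAP 6.2.5 deals only with missing dates.
- Protocol 12.7.3 covers the double-blind period only, and 12.7.4 has no TEAE definition.

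**3. Off-drug time counted as treatment-emergent**

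Formula: (last week followed − week stopped) × 7 days. The stopping weeks are assumed, with follow-up to Week 120.
- Fosmetpantotenate arm, stops at Week 3: 120 − 3 = 117 weeks = 819 days in the fosmetpantotenate table, against 1 day in the double-blind table.
- Open-label, stops at Week 27: 93 weeks = 651 days.
- Open-label, stops at Week 48: 72 weeks = 504 days.
- Open-label, stops at Week 96: 24 weeks = 168 days.
- Leaves the study at last dose: about 30 days, the end of capture.

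**4. Two classifications of one event**

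Take a fosmetpantotenate-arm patient who stops at Week 6. An event at Week 10 begins 28 days after last dose, and one at Week 12 begins 42 days after. Neither is a double-blind TEAE; both are fosmetpantotenate TEAEs. Ending the fosmetpantotenate window at 30 days removes the conflict for the Week 12 event (42 > 30) but not for the Week 10 event (28 < 30), unless the double-blind end is changed or the difference is explained.

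**5. A scale for the fosmetpantotenate table**

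The number who stop and stay is not given. As a scale only, take the SAP 4.2 allowance: 82 − 74 = 8 patients not completing the double-blind period.
- With 1:1 randomization about 4 of the 8 are on fosmetpantotenate.
- The table would hold 41 + (41 − 4) = 78 patients, assuming that every placebo completer takes open-label drug.
- 4/78 = 5.13%.

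Assume background rates of 0.25, 0.5 and 1 event per patient-year, and off-drug follow-up of 48 or 96 weeks (0.92 or 1.84 years). P(at least one event) = 1 − exp(−rate × years).

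| Follow-up | P at 0.25 / 0.5 / 1 | × 4/78, percentage points |
|---|---|---|
| 48 weeks | 0.205 / 0.369 / 0.601 | 1.1 / 1.9 / 3.1 |
| 96 weeks | 0.369 / 0.601 / 0.841 | 1.9 / 3.1 / 4.3 |

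These are upper values for those rates. They assume that none of the four patients had such an event on drug, and each patient is counted once per term.

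**The case against.** The strongest reply is that SAP 4.12.2 carries the double-blind counting rules over to the open-label period, and those rules include an end. That sentence is too general to override the explicit open-label definition in 4.11.1, and it leaves the Fosmetpantotenate Safety Population untouched.

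A second reply is that an open window is conservative for safety, and that the listings show onset dates. Both statements are true. But the SAP says so expressly where it intends a worst-case rule (missing severity, causality or dates), and it does not say so here. An off-treatment column would keep every event visible without mislabelling the percentages.

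Four stronger readings are tempting, and the documents do not support them.
- A reader might infer that the windows run indefinitely. In practice they end with adverse-event capture or the data cutoff, and the overrun is about 30 days for patients who leave at last dose. Long overruns arise only in those who stop and stay.
- A reader might apply 8 of 82 to every table and obtain 2.0 to 8.2 percentage points. The 8 are double-blind non-completers. About half would be on placebo, and none who never took an open-label dose belongs to the Open-Label Safety Population.
- A reader might infer that the tables attribute late events to the drug. Treatment-emergent is a timing label; the investigator assesses causality separately and it is tabulated separately.
- A reader might locate the error in Protocol 12.7.4. That section only omits the end; the definitions at fault are in SAP 4.11.1.

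**Conclusion.** The point holds as a defect in SAP 4.11.1 and is worth correcting. Applied as written, two of the three TEAE definitions count off-drug events as treatment-emergent, and the same event can be classified differently in two tables of one report.

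Its size cannot be computed from the documents, which give neither the number of patients who stop and stay nor an off-drug event rate. Under the assumptions shown, the upper value for the fosmetpantotenate table is about 1 to 4 percentage points. It would be lower if few patients reach 48 weeks off drug by the interim cutoff. No figure can be given for the open-label table, because the number stopping in that period is not stated. The primary efficacy analysis is unaffected.

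**What to change.** In SAP 4.11.1:

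1. End the open-label and Fosmetpantotenate Safety Population windows at a stated interval after the patient's last fosmetpantotenate dose. Thirty days is one choice, matching the post-dose capture period in Protocol 10.5.1.
2. Align the double-blind end with it, as the earlier of that interval after the last double-blind dose and the first open-label dose. Alternatively, keep the one-day end and footnote the difference in the tables. If the end is aligned, record it in the SAP as a departure from the definition in Protocol 12.7.3.
3. Tabulate later-onset AEs, SAEs and deaths in a separate off-treatment column, and keep them in the listings.

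No Protocol change is needed, because the Protocol defines no open-label TEAE window. The cost is a few sentences and one table column. The downside is small: a true effect whose onset falls after the window moves to the off-treatment column, where it remains visible.

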12.8. Pharmacokinetic Analyses

Multiple-dose blood concentrations of fosmetpantotenate will be tabulated and summarized by dose cohort and sample time. Concentration measures may also be analyzed by nonlinear mixed-effects modeling, either alone or in conjunction with data from other studies. Available metabolite concentrations will be analyzed similarly. Summarizations will include appropriate descriptive statistics (eg, n, geometric mean, coefficient of variation, minimum, median, maximum).

12.9. Efficacy

12.9.1. Double-Blind Period

The primary efficacy analysis will be based on the FAS population defined for the double-blind period of the study (see [Section 12.3](#)). For each patient, the change from Baseline in PKAN-ADL scores at Weeks 3, 6, 12, 18, and 24 of the double-blind period will be used for analysis. The treatment effect will be evaluated on the basis of mixed model for repeated measures (MMRM) analysis to assess data from all visits simultaneously. The model will include fixed effects for treatment, age stratum (6 to <18 or 18 to 65 years), visit and treatment by-visit interaction, a random effect for patient within treatment group, and Baseline

PKAN-ADL score as a covariate. The PKAN-ADL measurement obtained prior to the first dose of investigational product will serve as each patient's Baseline value. Least-squares adjusted means and the adjusted mean difference between treatment groups will be reported at each study visit, along with 2-sided 95% confidence intervals (CIs) and the p-value for the treatment comparison.

The mixed-effect linear model will be implemented using PROC MIXED in SAS with the restricted maximum likelihood (REML) estimation method and Kenward-Roger degrees of freedom algorithm for the F-test. Significance tests will be based on least squares means using Type III sum of squares.

To support the primary efficacy analysis, analysis of covariance (ANCOVA) models will be applied to change from Baseline in PKAN-ADL scores assessed after 3, 6, 12, 18, and 24 weeks of treatment. For each week analyzed, the model will include treatment and age stratum (6 to <18 or 18 to 65 years) as fixed effects and Baseline PKAN-ADL score as a covariate. Estimates of the adjusted mean treatment differences and the 2-sided 95% CIs at each time point will be obtained from the model.

Secondary and exploratory efficacy endpoints that are continuous measures recorded at each study visit will be evaluated using the MMRM approach described above for the primary efficacy endpoint. Summary statistics for efficacy measures will include graphical plots of mean and mean change from Baseline values at each study visit, by treatment group.

Treatment effects on categorical outcomes will be examined using frequency tables and tested using Cochran-Mantel-Haenszel chi-square methods with stratification by age group (6 to <18 or 18 to 65 years).

